guidelines change, or are not followed adequately, treatment-emergent events will be identified programmatically per the above definition, using imputed start date.

Severity of AEs will be reported using the NCI CTCAE grades (v4.03) where Grade 1 is Mild, Grade 2 is Moderate, Grade 3 is Severe, Grade 4 is Life-Threatening, and Grade 5 is Fatal.

CCI

CCI

B. Other Safety Parameters

Changes in vital signs, laboratory values and ECGs will also be evaluated and assessed. Information on the timing of these assessments is presented in Protocol Section 9.

The following laboratory tests will be conducted:

- Complete blood counts (CBC) and differential
- Coagulation
- Chemistry panel including LFTs (AST, ALT, INR, total bilirubin, gamma glutamyltransferase (GGT), and albumin)
- Urinalysis with microscopy
- ECGs

Laboratory values will be listed and summarized at each assessment. Numerical laboratory results will be summarized with the actual values, change from baseline (CFB), percent CFB by visit. P-value for test to assess maximum and minimum change from baseline within each cohort will be calculated using paired t-test.

Shift tables for laboratory values with respect to normal range (low, normal, high) and CTCAE toxicity grade, compared to baseline, will be summarized by visit. Overall laboratory result shift from baseline (Normal, Abnormal clinically significant (CS), and Abnormal non-clinically significant (NSC)) will be summarized.

ECG parameters and vital sign assessments will be summarized with the actual values, change from baseline, and percent change from baseline by visit. P-value for test to assess maximum and minimum change from baseline within each cohort will be calculated using paired t-test. Additionally, overall ECG result shift from baseline (Normal, Abnormal clinically significant (CS), and Abnormal non-clinically significant (NSC)) will be summarized.

Physical exam data will be listed.

X. Additional Analysis

The additional analyses outlined here will be performed using the Safety Population.

A. Pharmacodynamics

Pharmacodynamics (PD) obtained from serial blood, bone marrow, and urine sampling at specified time points will be listed and summarized.

CCI

CCI

CCI

The assessment value, change from baseline and percentage change from baseline of these parameters will be summarized by each treatment cohort and visit. P-value for test to assess maximum and minimum change from baseline within each cohort will be calculated using paired t-test.

Additionally, maximum change from baseline, maximum percentage change from baseline, minimum change from baseline, and minimum percentage change from baseline for these parameters will be analyzed in the dose-finding cohorts separately. The treatment effect among different cohorts will be analyzed with Kruskal-Wallis tests.

B. Exposure

Exposure to IMG-7289 and ATRA will be summarized separately (i.e., by drug). Exposure will be summarized as the number of doses each patient received, as well as number of missed doses, along with the reasons for the missed doses (if feasible). Average number of cycles and total amount of time on study drug (duration of dosing in weeks) will also be summarized. Total cumulative dose, dose intensity (mg/-week, calculated as [total cumulative dose (mg-) / duration of dosing (weeks)]), and relative dose intensity (% of planned, calculated as [total cumulative dose / total planned dose] *100) will also be derived and summarized with descriptive statistics for IMG-7289 and ATRA separately.

Dose adjustments (increases and decreases), interruptions, and permanent drug withdrawals, along with corresponding reasons for each, will be summarized by study drug (IMG-7289 and ATRA).

Study drug accountability by dosage strength will be summarized based on the number of capsules of study drug (IMG-7289 or ATRA) dispensed and the number of capsules returned.

All exposure data will also be listed by cohort and patient.

C. Prior and Concomitant Medications

Prior medication is defined as any medication with a stop date prior to the date of first dose of IMG-7289. Concomitant medications are defined as medications or therapies with a start date on or after the first dose of IMG-7289. Medications may be flagged as both prior and concomitant if the start date is prior to the date of the first dose of IMG-7289 and the medication continued after the first dose of IMG-7289. The medications will be coded using the most updated version of WHO Drug at the time of study initiation (up-versioning will not occur) and will be listed by cohort and by patient. The number (%) of patients using prior, prior and concomitant, and concomitant medications will be summarized.

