The patient population will consist of men and women age 18 or older who have been diagnosed with either high-risk Acute Myeloid Leukaemia or Myelodysplastic Syndrome. Eligible patients who have signed informed consent must not have had prior treatments within a specified period of time and must have meet pre-specified laboratory values for selected parameters, in addition to multiple other required eligibility criteria.

C. Sample Size Predictions

This study is designed to make an assessment of the safety, tolerability, and single-dose pharmacokinetics of the capsule formulation of IMG-7289, with and without ATRA. With the planned minimum number of patients per dose cohort/sub-cohort (N=3), the study is sufficiently powered to determine mean pharmacokinetic parameters. When feasible, more patients will be added to each cohort/sub-cohort. Approximately 40 patients with high risk AML/MDS patients will be enrolled and treated in this study.

D. Treatment Randomization

This is not a randomized study.

E. Assessment Schedule

The study assessments depend upon the cohort and the recommendations of the DSMC. Further description is available in the Protocol Sections 9 and 16.1.

V. Interventions

A. Clinical Trial Material

CCI
CCI
[REDACTED] IMG-7289 will be supplied in capsules of multiple strengths. These strengths, based on IMG-7289 free base, i.e. the active substance, may include: 5 mg, 10 mg, 25 mg, and 50 mg. Additional strengths may be added over the duration of the study.

ATRA will be supplied as oval, soft gelatin capsules; one half of each capsule is opaque orange-yellow and the other half opaque reddish brown. One capsule strength will be provided: 10 mg. In addition to ATRA, the capsule contents are beeswax-yellow, soya oil-hydrogenated and soya oil. The capsule shell contains gelatin, glycerol, Karion 83, titanium dioxide, iron oxide yellow CII77492 and iron oxide red CI77491.

The protocol provides additional product details in Protocol Section 7.

B. Study Procedures

Patients will undergo procedures described in Protocol Section 9 to assess the study drug safety, pharmacodynamics, and pharmacokinetics in order to achieve the study objectives.

VI. General Analytical Considerations

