The statistical analyses will be reported using summary tables, figures, and data listings. Unless otherwise noted, all statistical testing will be two-sided with significance being $p < 0.05$. Continuous variables will be summarized with means, standard deviations, medians, minimums, and maximums. Categorical variables will be summarized by counts and by percentage of patients in corresponding categories. As appropriate and where specified, continuous and categorical variables will be evaluated using the Student t-test, ANOVA, Wilcoxon rank sum, Fisher's exact, or χ^2 tests. As appropriate and where specified, summary tables will be presented by cohort, and may also include a "Total" or "All Patients" summary.

The analyses described in this plan are considered *a priori*, in that they have been defined prior to database lock. If any post-hoc analyses are performed they will be defined and reported in the CSR.

All analyses will be performed using SAS statistical analysis software (SAS, SAS/GRAPH and SAS/STAT; version 9.3 or higher of SAS for Windows [SAS Institute Inc; Cary, NC, USA]).

A. Data Sources

All data are collected *via* electronic case report forms (eCRFs) through remote data entry. Section 13.7 of the protocol describes data quality assurance.

B. Definition of Baseline

For analysis purposes, baseline is defined as the last assessment prior to the first dose of study drug. Cycle 1 Day 1 is the first day a patient receives study drug. For most measurements, baseline assessments will be taken pre-dose on Cycle 1 Day 1. If pre-dose assessments on Day 1 are not available, the most recent prior assessment closest to Day 1 may be substituted in some cases, and unless otherwise specified. For local laboratory data, baseline data will be obtained during the screening period (Days -28 to 1). All other baseline data will be collected on Days -21 to 1.

C. Missing Data

For safety and tolerability, missing data, including those not obtained because of death, will be the last value carried forward.

If CTCAE Grade is missing, the event is assumed to be 'Severe' (grade 3). If AE relatedness is missing, the event is assumed to be 'possibly' related.

Otherwise, missing data will not be replaced with imputed values. When relevant, sections below will address how missing data will be handled for the particular analyses.

D. Display and Imputation Methods for Missing Dates

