Data displays produced for this study will include three types—summary tables, data listings, and figures. Unless stated otherwise, data listings will be produced for all recorded data. In general, there will be one set of data displays encompassing patients in both the dose-finding phase and duration-finding phases. Summary tables will include columns for each cohort, and the ordering of these cohorts will be defined in the tables, listings, and figures (TLF) shells document. Summary tables will be produced as specified in the following sections. Additional data listings will be produced for outcome measures that involve extensive procedures to derive the analyzed outcomes.

Data listings will simply list the data that are either recorded on the CRF or derived for each patient. In general, they will be ordered by cohort, site, patient number, and time of assessment, unless otherwise specified in the display shell. When expedient, additional levels of ordering hierarchy may reflect subsets of assessments within patient. Data listings will not display patient initials.

Summary tables will display summary statistics calculated for each cohort, and for all patients combined, unless described otherwise in the following sections, or in the display shells. For most summary tables, the cohorts will be presented in a column, and the summary statistics of interest will be presented in rows.

Descriptive statistics (arithmetic mean, standard deviation (SD), sample size, median, minimum, maximum, and number) will be calculated for quantitative safety data as well as for the differences to baseline, when appropriate. In addition, shift tables for laboratory values with respect to normal range (low, normal, high) will be summarized; and overall laboratory and ECG result shift from baseline (Normal, Abnormal clinically significant (CS), and Abnormal non-clinically significant (NSC)) will be summarized.

Chi-square (χ^2), Fisher exact, and Kruskal-Wallis tests may be used to assess the significance of differences in haematologic and pharmacodynamics markers among the dose-finding and duration-finding cohorts. If applicable, event free survival (EFS), and overall survival (OS) will be calculated using the Kaplan-Meier method.

VII. Patient Accountability

A. Patient Characteristics

Demography. Data collected about the following patient characteristics at the screening/baseline visit will be listed and summarized for the safety population:

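### The Kruskal-Wallis comparison of dose-finding cohorts needs exact p-values: with the usual chi-square reference and 3 patients per cohort, its true level is about 2%, not the stated 5%, and power is lost

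*SAP*

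**What the plan says.** SAP VI sets one rule for all tests: two-sided, significant below 0.05. Its general list says that "continuous and categorical variables will be evaluated using the Student t-test, ANOVA, Wilcoxon rank sum, Fisher's exact, or" chi-square tests, with the qualifier that this holds only where suitable and where a test has been specified. Kruskal-Wallis is not in that list.

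Kruskal-Wallis appears in two later places. SAP X.A takes the maximum and minimum change (absolute and percentage) of each pharmacodynamic marker in the dose-finding cohorts and then says: "The treatment effect among different cohorts will be analyzed with Kruskal-Wallis tests". SAP VI.K is permissive and names three tests together, namely chi-square, Fisher and Kruskal-Wallis: "tests may be used to assess the significance of differences in haematologic and pharmacodynamics markers among the dose-finding and duration-finding cohorts". It does not say which test goes with which variable. Protocol 12.7 carries the same sentence.

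SAP IV.C gives 3 as the planned minimum per cohort and adds: "When feasible, more patients will be added to each cohort/sub-cohort". The total is about 40. SAP VI names SAS as the software but no exact or Monte Carlo option. SAP VI.I plans no multiplicity control.

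**The concern.** The usual Kruskal-Wallis p-value refers the statistic to a chi-square distribution, which is a large-sample approximation. With 3 patients per cohort it is poor in the tail, so a rule of p<0.05 does not give a 5% test. Adequacy of dose and duration in producing a pharmacodynamic effect is a primary objective, and X.A is the readable SAP's firm between-cohort test of pharmacodynamic markers. A test run well below its stated level will miss dose effects that the same data could show. For proportions, leaving both chi-square and Fisher open lets the decision depend on a choice made after the data are seen.

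**Working it through.** **Inputs.** Level 0.05, two-sided (SAP VI). Minimum n = 3 per cohort, possibly more (SAP IV.C). Number of dose-finding sub-cohorts k: 1a to 1d or 1a to 1e gives 4 or 5 (Protocol Table 1); adding 1χ and 1w gives 6 or 7 (Protocol Table 2). Assumed: equal cohort sizes, no ties, and the chi-square p-value.

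**The plan's own figure.** The only checkable figure is the 5% level, because the documents give no power calculation for this test. With N = kn and rank sums R_i,

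H = 12 / [N(N+1)] × Σ R_i²/n − 3(N+1),

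and the approximate test rejects when H exceeds the 95% point of chi-square with k−1 degrees of freedom. For k = 4 and n = 3, all rank allocations were counted: H passes the critical value in 2.05% of them. The stated 5% is not reproduced. The other cells below were simulated under the null hypothesis with 200,000 or more draws each.

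| n per cohort | 4 cohorts | 5 cohorts | 6 cohorts | 7 cohorts |
|---|---|---|---|---|
| 3 | 2.1% | 1.9% | 1.9% | 1.8% |
| 4 | 3.4% | 3.1% | 3.0% | 2.8% |
| 5 | 3.8% | 3.6% | 3.5% | 3.4% |
| 6 | 4.1% | 3.9% | 3.8% | 3.7% |

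**What exact p-values do at n = 3.** With 4 cohorts the exact test rejects from H = 7.0, where the chi-square p-value is 0.072; its attained level is 4.35%. With 5 cohorts it rejects from H = 8.33, where the chi-square p-value is 0.080, against a chi-square critical value of 9.49; its attained level is about 4.95%. Results between these cut-offs are significant by exact test and not by the approximation.

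**Power.** Five cohorts of 3, normal data with equal SD, and a constant shift per dose step. The shifts are assumptions, since the documents give none.

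| Shift per step | Chi-square reference | Exact |
|---|---|---|
| 0.5 SD | 20% | 36% |
| 0.75 SD | 51% | 71% |
| 1.0 SD | 81% | 93% |

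**Chi-square against Fisher.** The smallest illustration is 3/3 v 0/3. All expected counts are 1.5, so chi-square = 4 × 1.5²/1.5 = 6.0 on 1 df, p = 0.014. Fisher: 2/20 = 0.10.

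The same happens among several cohorts, which is the comparison VI.K describes. Take 4 cohorts of 3 with 3/3, 1/3, 0/3 and 0/3. The expected counts are 1 responder and 2 non-responders per cohort. Chi-square = (4+0+1+1)/1 + (4+0+1+1)/2 = 9.0 on 3 df, p = 0.029. For the Fisher-Freeman-Halton test there are C(12,4) = 495 ways to place 4 responders. The observed table has weight 3, and the only tables this unlikely are its 12 arrangements, so p = 12 × 3/495 = 0.073. The two tests give opposite decisions on the same data.

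**The case against.** Several objections have force.

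- **The p-value type is not stated.** The SAP does not say asymptotic, SAS offers exact options, display details are left to a shells document, and text just before the X.A analysis is blacked out. This stands, so the levels above are conditional on the chi-square reference.
- **Three is a floor.** The described pathways, with one 14-day and one 21-day cohort, give 8 or 9 cohorts; 40/9 = 4.4 and 40/8 = 5.0 patients on average. At 4 or 5 per cohort the level is 2.8 to 3.8%. The defect shrinks but does not vanish.
- **The consequence is limited.** VI.K says only that the tests may be used, the study is not randomised, and escalation follows DLT counts and DSMC review. Response is reported with an exact confidence interval. This stands too.
- **Chi-square is not too lenient at 3 v 3.** Uncorrected, only 3/3 v 0/3 is significant, so its level is 2p³(1−p)³, at most 2/64 = 3.1%. The fault in VI.K is the open choice, not an inflated error rate in that case.

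Stronger readings are tempting but not supported. A reader might infer that a comparison of two duration cohorts of 3 would run at 10% (2 of 20 allocations reach p = 0.0495). No pairwise duration test is specified, and X.A confines its analysis to the dose-finding cohorts. A reader might also see a conflict between Kruskal-Wallis and the t-test, ANOVA or Wilcoxon test in SAP VI. That list is generic and applies only where specified. No readable section assigns those tests to a between-cohort comparison, and the t-tests in IX.B and X.A are paired and within cohort. For the same reason nothing calls for banning ANOVA or t-tests, which hold 5% under normality in simulation.

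**Conclusion.** The point holds in a limited form. Under the chi-square reference, the Kruskal-Wallis test fixed in X.A runs at about 2% with 3 patients per cohort and 4 to 7 cohorts, and at roughly 3 to 4% with 4 to 6 per cohort. It is conservative throughout that range. In the scenarios tried, with 5 cohorts of 3, the loss against exact p-values is 12 to 20 percentage points of power. Separately, VI.K leaves open two tests for proportions that can disagree at this size. The results assume equal cohorts, no ties and, for power, normal data with assumed shifts. This is a cheap improvement to how markers are reported. It does not show inflated error rates, and it does not touch dose decisions.

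**What to change.** In SAP X.A and VI.K, state: *Kruskal-Wallis p-values for comparisons among cohorts will be exact, or Monte Carlo estimates of the exact value. Between-cohort comparisons of proportions will use Fisher's exact test (Fisher-Freeman-Halton for more than two cohorts) in place of chi-square.* The SAP may be modified until database lock, so this can be made there.

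The cost is two sentences, an exact option in the SAS code and some computing time. The statistical downside is that any comparison of two cohorts of 3 cannot reach p<0.05, since the smallest two-sided exact p-value is 2/20 = 0.10. Such comparisons would be reported by estimates only, and the SAP should say so.

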12.5 Safety and Tolerability Data

Demographics will be tabulated and summarized. Medical and surgical history data at Screening will be listed, as will Physical Examination data (including height and weight) at Screening, and at subsequent visits. All characteristics at Baseline such as age, weight, height, vital signs (resting heart rate, semi-supine systolic/diastolic blood pressure, respiratory rate and temperature), and ECG parameters will be tabulated and summarized.

All patients receiving at least one dose of IMG-7289 will be included in the safety analysis.

Laboratory values outside the laboratory normal ranges will be summarized and assessed for change from Day 1 and trends indicating a safety signal.

Treatment-emergent adverse events will be coded using the most updated version of Medical Dictionary for Regulatory Activities (MedDRA) available to the Sponsor at the time of study initiation (up-versioning will not occur) and summarized by cohort for the number of patients reporting the AE and the number of AEs reported. A by-patient AE data listing including (but not limited to) verbatim term, coded term, cohort, severity, and relationship to treatment will be provided.

Concomitant medications will be listed by patient and coded using the most updated version of WHO drug dictionary available to the Sponsor at the time of study initiation (up-versioning will not occur). Medical history will be listed by patient.

Descriptive statistics (arithmetic mean, standard deviation (SD), sample size, CV (coefficient of variation), median, minimum, maximum, and number) will be calculated for quantitative safety data as well as for the differences to baseline, when appropriate. In addition, a shift table describing out of normal range shifts will be provided for clinical laboratory results, and ECG tracings. Chi-square (χ^2), Fisher exact, and Kruskal-Wallis tests may be used to assess the significance of differences in baseline patient characteristics. For safety and tolerability, missing data including those not obtained because of death will be the last value carried forward.

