The protocol (Section 4.1) lists the following hypothesis: IMG-7289 with and without all-*trans* retinoic acid (ATRA; tretinoin) is a safe and tolerable orally available agent when administered to patients with advanced myeloid malignancies including high risk AML and high risk MDS; LSDi by IMG-7289 will have a negative impact on leukaemic and dysplastic cells, an effect which may be further enhanced *via* synergistic mechanisms when administered in combination with ATRA.

B. Primary

The protocol (Section 4.2) lists the following primary objectives:

- Safety and tolerability
- Pharmacokinetics
- The adequacy of dose and duration in producing a pharmacodynamic effect

C. Secondary

The protocol (Section 4.2) lists the following secondary objectives:

- The association of plasma concentrations (C_{\max} and C_{\min}) and exposure (AUC) on haematopoiesis (both short and longer-term measures)
- The kinetics of recovery of haematopoiesis for a given dose and for a given duration of dosing

CCI

III. Study Endpoints

A. Primary

[figure not shown]
The safety and tolerability of IMG-7289 with and without ATRA will be assessed by the analysis of adverse events (AEs), as well as changes in physical examinations, vital signs and laboratory values as detailed below.

- Monitoring of Adverse Events (AEs) including determination of dose limiting toxicities (DLTs), medical events of interest (MEOIs), serious adverse events (SAEs), and AEs. AEs will be assessed in terms of onset, duration, seriousness, severity, and causality, using the National Cancer Institute Common Terminology Criteria for Adverse Events (NCI CTCAE), Version 4.03. Deaths and other serious adverse events (SAEs) will also be evaluated and will be collected on a separate case report form (CRF).
- Changes in physical examinations, vital signs and laboratory values will also be evaluated and assessed. Information on the timing of these assessments is presented in Protocol Section 9. The following laboratory tests will be conducted:
 - Complete blood counts (CBC) and differential
 - Coagulation
 - Chemistry panel including LFTs (AST, ALT, INR, total bilirubin, gamma glutamyltransferase (GGT), and albumin)
 - Urinalysis with microscopy
 - Electrocardiograms

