- Therapies that are not marked as ongoing, and have a stop date with a missing day and month will be assumed to occur on the *last* day of the non-missing year (i.e. December 31).

For the listings, AE, CM and PCTHX dates will be listed as collected in the eCRF. All other data will be reported as they are collected. No imputation methods will be used to replace missing data unless otherwise stated in this document.

Partial transfusion start dates are not permitted, and thus assumptions should not be needed to determine if the transfusion was prior to the first dose of IMG-7289.

E. Multiple Study Centers

There will be no adjustment for multiple study centers in the analysis.

F. Covariate Adjustment in Primary Analysis

There will be no adjustment in the analysis for covariates.

G. Sample Size Reassessment

No sample size reassessment is planned for this study.

H. Interim Analyses or Timing of Analyses

The Data Safety Monitoring Committee (DSMC) will review safety parameters, pharmacodynamic markers, and pharmacokinetic parameters to draw conclusions around the safety and pharmacodynamic effect of differing doses, treatment regimens and dosing durations. DSMC reviews are critical, as neither a new dose-finding sub-cohort, nor a duration-finding cohort may commence without DSMC review and recommendation to do so. Refer to Protocol Section 8 for details pertaining to DSMC reviews, and management of study toxicities.

I. Multiple Comparisons

No control for the effect of multiple comparisons is planned.

J. Analysis Populations

Two analysis populations will be defined for use with various analyses.

1. Safety Population

All enrolled patients who received at least one dose of IMG-7289 will be included in the Safety population.

2. Efficacy Population

All enrolled patients who received at least one dose of IMG-7289 and have disease assessment at baseline (Bone Marrow Aspirate/Biopsy and Haematology). Patients having no post-baseline response assessment will be defined as NE (Not Evaluable).

K. Data Display Characteristics

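### Missing safety data are carried forward with no stop at death, so by-visit laboratory, vital-sign and ECG tables would, as written, include values for patients who have died

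*SAP*

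**What the plan says.** **The rule.** SAP VI.C (Missing Data): "For safety and tolerability, missing data, including those not obtained because of death, will be the last value carried forward". Protocol 12.5 has the same sentence: "For safety and tolerability, missing data including those not obtained because of death will be the last value carried forward". Neither sets an end point such as death, study exit, a last planned visit or a maximum gap.

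**The default around it.** After the carry-forward rule and two rules for missing adverse event grade and relatedness, SAP VI.C says that other missing data are left unimputed and that later sections will deal with missing data where needed. SAP VI.D adds: "No imputation methods will be used to replace missing data unless otherwise stated in this document".

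**The tables it reaches.** All are in SAP IX.B:
- Laboratory values: "Numerical laboratory results will be summarized with the actual values, change from baseline (CFB), percent CFB by visit".
- Laboratory shift tables, by normal range "and CTCAE toxicity grade, compared to baseline, will be summarized by visit".
- ECG and vital signs: "ECG parameters and vital sign assessments will be summarized with the actual values, change from baseline, and percent change from baseline by visit".

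**The patients in them.** SAP IX uses the Safety Population. SAP VI.J defines it: "All enrolled patients who received at least one dose of IMG-7289 will be included in the Safety population". Nobody is removed at death.

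**Status of the measures.** SAP III.A lists them under the primary safety endpoint: "Changes in physical examinations, vital signs and laboratory values will also be evaluated and assessed".

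**The concern.** A by-visit safety table should describe the patients measured at that visit. Under this rule, a patient who dies keeps contributing the last pre-death value at later visits. The table then shows a full n where fewer patients were measured, and its mean, SD and CTCAE grade distribution mix measured and copied values.

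Two features of the trial make this more than a technicality.
- Groups can be as small as 3, so one copied value carries real weight.
- Treatment is given in on/off cycles, and Protocol 8.2.1 expects marked but reversible cytopenias with rapid recovery that overshoots baseline. A count from one phase of a cycle is a poor stand-in for a rest-period or follow-up visit.

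Deaths on study are foreseeable. The population has high-risk AML or MDS, entry requires a life expectancy above 12 weeks, and Cohort 1 participation runs about 15 weeks from first to last visit. The documents give no death rate.

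**Working it through.** The plan gives no figure on this point, so there is none to reproduce. The check is a reading of the text followed by simple counts.

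**1. Does the rule run past death?** It classes data lost through death as missing and fills them. The only data that death can make missing are those due after it, so the clause has no function unless values are carried past death.

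**2. Does anything cancel it?** The unimputed default in SAP VI.C covers only what the rule leaves out. The SAP VI.D sentence yields to anything stated elsewhere in the SAP, and VI.C is such a statement. The visible text of SAP IX.B has no missing-data handling.

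**3. Weight of one deceased patient in a by-visit summary.** Share copied = k/N, with k = 1.

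| N | Source | Share |
|---|---|---|
| 3 | minimum group size, Protocol 12.2 and SAP IV.C | 1/3 = 33% |
| 6 | illustration; more patients may be added | 1/6 = 17% |
| 40 | approximate total, all-patients column (SAP VI.K) | 1/40 = 2.5% |

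The mean moves by (k/N) × (copied value − mean of measured values). Example with invented numbers: two survivors have changes from baseline of +10 and +5 (mean 7.5), and the deceased patient's carried change is −40. The shift is (1/3) × (−40 − 7.5) = −15.8, so the table shows −8.3 on n = 3 instead of 7.5 on n = 2. A carried value above the survivors' mean would shift it the other way.

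**4. Haematology time points filled after one death.** Assume the patient dies just after the Day 1 sample of the last initial cycle and would have left the study after that cycle.
- Cohort 1, Cycle 4 (Protocol 16.1.3): Days 4, 7, 9, 11 and 14 remain, which is 5. Footnote h replaces Day 14 with the EOT visit, so follow-up adds only pre-EOS and EOS: 5 + 2 = 7.
- Cohort 3/3χ, Cycle 2 (Protocol 16.1.5): Days 4, 7, 10, 12, 14, 16, 18 and 21 remain, which is 8. Footnote e replaces Day 21 with EOT: 8 + 2 = 10.

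Haematology is the most-sampled laboratory panel. Coagulation, standard biochemistry and urinalysis fall on pre-dose Day 1, Day 7 and Day 14 in Cohort 1, giving 2 + 2 = 4. In Cohort 3/3χ they fall on pre-dose Day 1 and Days 7, 14 and 21, giving 3 + 2 = 5. ECGs are required only in the first 9 patients (Protocol 8.1), and the Cohort 1 Cycles 2-4 schedule has no ECG row, so their exposure is smaller.

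These counts are not ceilings. If cycles never started also count as missing, a Cohort 1 death at the end of Cycle 1 gives 6 × 3 + 2 = 20. Additional cycles are open-ended, so no upper bound exists.

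**5. How often?** As an assumption only, take an independent on-study death risk p per patient. The chance that a cohort of 3 has at least one death is 1 − (1 − p)³:
- p = 5%: 14%
- p = 10%: 27%
- p = 20%: 49%
- p = 30%: 66%

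**6. What does not change?** Repeating an observed value cannot alter a patient's maximum or minimum, so the paired t-tests on maximum and minimum change are unaffected. The exception is a patient with no post-baseline value, who would enter with zero change if baseline is carried forward. Adverse event and DLT counts and overall survival do not use carried values, escalation follows DLT counts and DSMC review, and listings show recorded data.

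**The case against.** **The effect is limited.** These are descriptive tables in an open-label, non-randomised study, and the listings keep the measured values visible. This stands. It means that the point does not threaten the trial's safety conclusions. A reader might infer that the primary safety endpoint or dose escalation is compromised, but the documents do not support that: adverse events, DLTs and DSMC decisions do not pass through this rule.

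**It may be handled elsewhere.** SAP VI.C promises later handling where relevant, the display layout is left to shells that are not public, and text just before SAP IX.B is redacted. A sensible programmer might also stop at death. This limits certainty about what will be produced, but the visible instruction says otherwise, and a silent departure from it would be a deviation from the plan.

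**Patients who leave alive.** A reader might infer that they too are filled in through every remaining cycle. The text does not settle this. Protocol 6.7 asks them back for follow-up visits, where laboratory values and vital signs are measured, and the number of cycles is a maximum. Copies arise in unstarted cycles only if those visits count as missing, so this part is secondary.

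**Direction.** A reader might infer that the rule flatters the drug. The last value may be worse or better than the survivors' values, so the direction of bias is unknown.

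**The remedy may go too far.** Dropping carry-forward altogether also removes it for an isolated missed visit in a patient still on study, which is more than the defect requires. This is fair, and a narrower change is offered below.

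**Cost and importance pull apart.** The measures sit under the primary endpoint, yet the change is treated as minor. This is also fair, and the sponsor should record its judgement.

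**Conclusion.** The point holds and should be fixed. As written, the by-visit laboratory, vital-sign and ECG summaries and the by-visit laboratory shift tables would include values for patients who have died, with an n that is not the number measured. This is a stated rule that gives a wrong result, and it appears in both documents.

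The size depends on group size. The 33% figure applies only at the minimum of 3 and falls as patients are added. The counts of 7 and 10 assume a death just after Day 1 of the last initial cycle and no additional cycles. They are illustrations, and no expected number of copies can be given.

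Confidence is high that the visible text sets no stop at death. It is lower on what the final tables will contain.

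**What to change.** Replace the carry-forward sentence in SAP VI.C with wording such as:

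> Missing laboratory, vital-sign and ECG values are not imputed. By-visit summaries and by-visit laboratory shift tables use observed values and show the number of patients measured at each visit. No value is included after death or study exit.

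At minimum, keep the rule but end it at death or study exit. Leave the separate rules for missing CTCAE grade and adverse event relatedness as they are. Optional additions are cumulative deaths and discontinuations by visit, and a shift table of worst post-baseline CTCAE grade.

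**Cost.** This is one sentence in a SAP that may be changed until database lock (SAP I.B), and slightly less programming. Protocol 12.1 lets the SAP modify the protocol's plans but asks for an amendment when a change to the primary endpoint or its analysis is major. A missing-data rule for descriptive tables reads as not major, but the sponsor should record that decision. If it is not major, Protocol 12.5 can be aligned at the next amendment, since protocol changes need written HREC approval (Protocol 14.1).

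**Downside.** Later visits will show a smaller n, and their means will describe only patients still observed. A table footnote should say so.
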